9.1. Study design

This drug utilisation study for Flupirtine will employ an analysis using a longitudinal database in Germany:

- Patient level electronic medical record (EMR) data (IMS[®] Disease Analyzer)

The IMS[®] Disease Analyzer provides both drug use data and information about patients' clinical characteristics, including indication, co-morbidities and laboratory tests in separate physician panels.

The study will be carried out in Germany as more than 90% of total prescriptions of flupirtine-containing medicinal products of MAHs in European Union Member States were issued in Germany.

The study will be set up as a pre-post design to compare flupirtine prescribing patterns (before and after the revision of SmPC).

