9.3. Variables

The following variables will be derived from the data sources.

IMS[®] Disease Analyzer – PCP and orthopaedist panels

- Number of prescribing physicians
- Region of office (East/West Germany)
- Number of overall patients in the office
- Number of patients with at least one prescription of flupirtine-containing medicinal product
- Patient characteristics
 - Age
 - Gender
 - Insurance status (private or SHI insured)
 - Indication for Flupirtine exposureⁱⁱⁱ
- Flupirtine exposure
 - Number of Flupirtine prescriptions per patients during the observation period
 - Single use and repeated prescriptions
 - Treatment duration (by physician)
 - Dosage advice (by physician)
 - Prescription length (based on DDD or on physician's advice if available)
 - Co-diagnosis during study period
 - Concomitant prescription of drugs grouped by relevant ATC classesⁱⁱ
- Long-term medications (>14 days) leading to contraindication for Flupirtine
- Diseases contraindicated for NSAIDs and weak opioids
- Liverfunction tests - as far as available within 1 week after Flupirtine exposure

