9.7.2.3 Monitoring of liver function

For patients where liver function tests after Flupirtine exposure are available (within 1 week after Flupirtine prescription) the following tests will be analyzed in the PCP and orthopaedist panel. Although a feasibility check has shown that laboratory tests are more comprehensively covered in the PCP panel of the database than in the specialist panels, liver function test will also be monitored in the orthopaedist panel in order to ensure comprehensiveness of data.

However, the laboratory tests of the orthopaedist panel will only be included in the analysis in the case sufficient liver function test data are available. A minimum number of 100 laboratory test results per time period will be considered as sufficient.

As Flupirtine treated patients happen to have false positive Bilirubin results, Bilirubin will not be considered the analysis²¹

The proportion of prescriptions with at least one liver function tests within 1 week after prescription date of flupirtine will be estimated.

Liver function tests

- GOT
- GPT
- Gamma-GT
- AP
- Albumin

Analyses:

- Number and percentage of patients with test available
Value of the test

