9.7.2.4 Comparison of the patient/prescriptions of the two observational periods

The comparison of the patients/prescriptions of the two observational periods (assessment period and reference period) based on IMS[®] Disease Analyzer data will consider the following parameters. The comparisons will be performed separately by physician panel and will be stratified by incident and prevalent users:

- Number and percentage of patients with any diagnosis of disease contraindicated for NSAIDs or weak opioids
- Number and percentage of prescriptions with diagnosis associated with acute pain
- Number and percentage of patients with single and repeated flupirtine prescriptions within the defined time period
- Number and percentage of prescriptions with LFT monitoring during flupirtine treatment
- Length of treatment episodes
- Number and percentage of patients with at least one treatment episode longer than 14 days (based on DDD)

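### The liver-test proportion counts a test that is not in the database as a test not done, and nothing in the plan would show whether a 2012–2014 change reflects practice or laboratory capture

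*Protocol*

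**What the plan says.** Section 9.7.2.3 (Monitoring of liver function) defines the measure: "The proportion of prescriptions with at least one liver function tests within 1 week after prescription date of flupirtine will be estimated". It also lists "Number and percentage of patients with test available". Section 9.7.2.4 carries the measure into the before-and-after comparison as "Number and percentage of prescriptions with LFT monitoring during flupirtine treatment", one of six parameters there. The window is worded differently in the two sections, but in neither is the base restricted. Section 9.1 gives the purpose: "The study will be set up as a pre-post design to compare flupirtine prescribing patterns" before and after the SmPC revision.

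The protocol also concedes that laboratory data are incomplete. Section 9.3 lists liver tests only "as far as available within 1 week after Flupirtine exposure". Section 9.7.2.3 reports that "a feasibility check has shown that laboratory tests are more comprehensively covered in the PCP panel of the database than in the specialist panels". Section 9.9 says that care sought outside the practice is not recorded and that patients cannot be followed across panels.

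One safeguard is specific to this measure. Orthopaedist laboratory data are analysed only if there are enough of them: "A minimum number of 100 laboratory test results per time period will be considered as sufficient". Section 9.7.1 adds the general rule that missing values are reported as missing and not imputed.

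**The concern.** A prescription with no liver test on file can mean that no test was done, or that a test was done but did not reach this practice's record. The measure treats both as not monitored. The missing-value rule does not separate them, because an absent test leaves no field to mark as missing.

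Liver-function testing is one of the risk minimisation measures listed in section 7, and the study exists to show prescribing before and after those measures. If the recorded proportion moves between 2012 and 2014, the reader will take this as a change in physicians' behaviour. The plan reports nothing that would let anyone check whether laboratory capture moved instead.

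**Working it through.** **The plan's own figures.** No capture rate and no expected liver-test proportion is stated. The relevant stated figures are the panel sizes in Table 2 (section 9.5), after a 25% reduction:

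- PCP: 11,284 × 0.75 = 8,463, as printed.
- Orthopaedist: 1,821 × 0.75 = 1,365.75, printed as 1,365.

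**Is the base really all prescriptions?** The protocol does not use the word 'all'. The first sentence of section 9.7.2.3 speaks of patients for whom tests are available. If that were the base, the percentage of patients with a test available would be 100% by construction. The unrestricted base is the only workable reading.

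**Effect of capture.** Let p be the true share of prescriptions followed by a test, and c the share of those tests that reach the database. Then

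recorded proportion = p × c.

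Neither p nor c is in the documents, so all values below are assumptions. The intervals are Wald 95% intervals for a difference between two periods, with 8,463 units in each and one prescription per patient assumed:

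d ± 1.96 × √[a(1 − a)/n + b(1 − b)/n].

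| True p, 2012 and 2014 | Capture c, 2012 and 2014 | Recorded | Difference in points (95% CI) |
|---|---|---|---|
| 20%, 20% | 60%, 60% | 12%, 12% | 0 (−1.0 to 1.0) |
| 20%, 20% | 50%, 60% | 10%, 12% | 2.0 (1.1 to 2.9) |
| 20%, 20% | 50%, 70% | 10%, 14% | 4.0 (3.0 to 5.0) |
| 20%, 20% | 75%, 50% | 15%, 10% | −5.0 (−6.0 to −4.0) |
| 10%, 20% | 60%, 30% | 6%, 6% | 0 |

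For the third row: 0.20 × 0.50 = 0.10 and 0.20 × 0.70 = 0.14. The standard error is √[(0.10 × 0.90 + 0.14 × 0.86)/8,463] = 0.0050, so the half-width is 1.0 point. At this panel size, the confidence intervals that section 9.7.1 provides for would make an artefact look precise. The first row shows the other side: with stable capture there is no spurious difference, only a lower level (12% recorded against 20%). The last row shows that a real doubling can be hidden.

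**Does the 100-result rule help?** It counts results, not capture. Five tests are listed, so 100/5 = 20 patients with a full set meet it, and 20/1,365 = 1.5% of the expected orthopaedist patients. With one test each, 100/1,365 = 7.3%. Genuinely rare testing would fail the rule just as poor capture would. The rule does not apply to the PCP panel.

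**Comparison with other measures in the same protocol.** The analysis of contraindications to NSAIDs or weak opioids (section 9.7.2.1) uses only patients with at least 12 months of history. For treatment duration (section 9.7.2.2), the percentage of patients without information is reported. The liver-test measure has neither protection.

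**What a restricted base would leave.** If 40% to 75% of the 8,463 PCP units came from practices with laboratory results (assumed), 3,385 to 6,347 would remain. The 95% half-width, 1.96 × √[p(1 − p)/m], would be 0.7 to 1.0 points at p = 10%, 1.0 to 1.4 at p = 20%, and 1.2 to 1.7 at p = 40%. Precision in the PCP panel is not an obstacle.

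**The case against.** The strongest reply has four parts.

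- **It belongs in the statistical analysis plan.** Section 9.8 refers to such a plan with table shells, and exact denominators often sit there. This holds for the details of a practice flag. It does not dispose of the point, because the protocol itself fixes the unit, the numerator, a one-week window and the comparison, and concedes uneven coverage without linking it to the measure.
- **The mechanism is assumed.** A reader might infer that some practices deliver no laboratory data at all. The documents do not say so. Table 1 lists laboratory tests and results among the database variables, and better coverage in the PCP panel could partly reflect more tests being ordered there. A reader might also infer that capture changed between the two years. Nothing in the documents shows this. Both periods use the same database, and section 9.8 describes continuous checks of panel consistency. Both replies stand. What remains is that a change could not be detected.
- **The measure can also err upwards.** Any of the five tests within the week counts, whatever the reason for ordering it. This stands: the recorded figure is a floor for testing in that window, but not strictly for monitoring prompted by flupirtine.
- **Restricting the base has its own bias.** A practice that truly orders no tests would be dropped, and so, under a both-years rule, would one that began testing only after the SmPC revision. This stands, and it is why restriction should not become the main analysis.

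A reader might also see a distorted contrast between PCPs and orthopaedists. No such comparison is planned. Sections 9.7.1 and 9.7.2.4 keep the panels separate and compare periods within each, and the protocol discloses the coverage difference.

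**Conclusion.** The point holds in a limited form. The measure is the share of prescriptions with a recorded test, and the plan gives no means of telling 'not tested' from 'not captured'. The recorded level can therefore understate actual testing, and a 2012–2014 difference cannot be attributed to practice without information on capture.

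The size is unknown. The 10% against 14% example rests on an assumed 20% true monitoring rate, assumed capture of 50% and 70%, and capture acting as a simple multiplier. It shows what the design would fail to notice, not what happened. The study is descriptive and tests no hypothesis, so this is a cheap improvement to how one of its six comparisons can be read. It does not invalidate the study.

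**What to change.** In sections 9.7.2.3 and 9.7.2.4:

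1. Keep the proportion among all flupirtine prescriptions as the main figure, but label it as prescriptions with a recorded liver function test.
2. Report, for each panel and period, the number and share of practices, and of flupirtine prescriptions, with any laboratory result in the database (any type of test, any patient).
3. Add a sensitivity analysis of the before-and-after liver-test comparison, first in practices with any laboratory result in the period concerned, then in practices with such results in both periods.
4. State the limits of that analysis. The denominator is smaller. Practices that truly order no tests, or that began testing only after the SmPC revision, are lost, so the restricted figure may overstate monitoring. Tests done elsewhere and partial capture within a practice are not recovered.
5. In section 9.9, apply the existing remark on unrecorded outside care to this measure.

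The cost is one practice-level flag, built from laboratory data that Table 1 says the database holds, and a few extra table rows. If the unrestricted and restricted comparisons agree and the capture shares are stable, a reading as change in practice is better supported. If they differ, the report should say that the change cannot be attributed.

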Drug utilisation study (DUS) on flupirtine-containing medicinal products.

Retrospective drug utilisation study using patient-level databases to characterise prescribing practices of flupirtine-containing medicinal products during routine clinical use and assess the main reasons for prescription by representative groups of prescribers.

Rationale and background

Due to a rising number of hepatotoxicity reactions during treatment with flupirtine containing products the Co-ordination Group for Mutual Recognition and Decentralised Procedures – Human (CMDh) recommended on 28 June 2013 to restrict the use of oral Flupirtine medicines and suppositories as following:

- treatment of acute (short-term) pain in adults who cannot use other painkillers, such as non-steroidal anti-inflammatory drug (NSAIDs) and weak opioids
- treatment duration limited to not longer than 2 weeks
- after each full week of treatment patients' liver function should be checked
- treatment termination if any signs of liver problems occur
- contraindicated for patients with preexisting liver disease or alcohol abuse problems
- contraindicated for patients taking other medications known to cause liver problems

The recommendations follow a review by the EMA's Pharmacovigilance Risk Assessment Committee (PRAC) which looked into reported liver problems with Flupirtine, ranging from high liver-enzyme levels to liver failure. The PRAC evaluated the available data on liver safety, noting that there were no cases of liver failure or liver transplantation reported in patients who took the medicine for 2 weeks or less. The PRAC also reviewed the available data on the benefits of Flupirtine and concluded that, while there were data from studies in the treatment of acute pain, there were insufficient data to support its use in the treatment of long-term pain.

The CMDh agreed with the PRAC's conclusions and endorsed the PRAC's recommendations on the use of flupirtine-containing medicines. The CMDh position was sent to the European Commission (EC), which endorsed it and adopted a final legally binding decision valid throughout the EU on 5 September 2013.

The reported outcomes were communicated to healthcare professionals by all Germany marketing authorisation holders (MAHs) via a joint Direct Healthcare Professional Communication (DHPC) distributed in July 2013.

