The PRAC initiated a subsequent benefit-risk evaluation and considered that the controlled clinical studies required by the Note for guidance on clinical investigation of medicinal products for treatment of nociceptive pain (CPMP/EWP/612/00, issued 21 November 2002) for long-term treatment of chronic pain are not available for flupirtine-containing medicinal products². Based on the fact of observed liver effects recorded during long-treatment with Flupirtine and on the absence of controlled long-term clinical studies, the PRAC noted that the management of chronic pain is no longer favourable in terms of the benefit-risk balance for flupirtine-containing medicinal products. The PRAC adopted a recommendation on 13 June 2013 under the provisions of article 107i of Directive 2001/83/EC³.

Taking the currently available data into account, the PRAC decided that the benefit-risk balance for flupirtine-containing products is favourable in the treatment of acute pain, subject to implementation of the following risk minimisation measures⁴:

- Limitation of indication to acute pain in adults if treatment with other analgesics (e.g. NSAIDs, weak opioids) is contraindicated.
- Restriction of Flupirtine use to a maximum of two weeks of treatment.
- Contraindication of Flupirtine in patients with pre-existing liver disease or alcohol abuse.
- Contraindication of Flupirtine in patients concomitantly taking other medications which are known to cause Drug Induced Liver Injury (DILI).

- Weekly liver function tests during treatment and discontinuation in the case of abnormal liver function tests or clinical symptoms.

The PRAC imposed a DHPC, which was distributed on 15 July 2013, in order to communicate the outcome of the PRAC/EMA decision to healthcare professionals⁵. The SmPCs for flupirtine-containing medicinal products have been revised accordingly by Lupin in February 2014 and MAHS marketing flupirtine-containing medicinal products in September/October 2013⁶. The educational material was distributed in February 2015.

Patients and prescribers have been provided with joint educational material according to the PRAC request, prepared jointly by all German MAHs. The educational material, the DUS and a PASS protocol are parts of the RMP.

As of 5 September 2013, the European Commission implemented the decision (C(2013) 5788 final) with the majority opinion of the CMD(h) addressed to all member states based on the PRAC's recommendation⁷.

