Additionally the PRAC requested that the MAHs should submit a risk management plan (RMP) within 3 months after the EC decision. The protocols of two studies - a drug utilization study (DUS) and a PASS should be submitted as part of the RMP.

Hormosan Pharma GmbH launched Flupirtinmaleat-Hormosan 100 mg Hartkapseln in Germany on 31 July 2012, but the marketing of the product was stopped in January 2013. This decision was taken because of commercial and not for safety reasons. Any other MAs held by Lupin Group of companies within EU have not been launched yet. Therefore an extension of deadline for submitting the RMP (including the outline of DUS, PASS and educational material) was received by the Reference Member State (RMS) authority BfArM on 29 November 2013 as the products are currently not marketed.

This protocol covers a design for a DUS based on the information captured in longitudinal patient-level databases and has been designed to fulfill the conditions of the authority.

8. Research question and objectives

The Flupirtine DUS aims to characterise prescribing practices of flupirtine-medicinal products during routine clinical use and to assess the main reasons for prescription by representative groups of prescribers.

The analysis will display by specialty and by prevalent/incident status:

- Number of prescribing physicians
- Region of office (East/West Germany)
- Number of overall patients in the office
- Number of patients with at least one flupirtine containing product

- Patient characteristics: age, gender, insurance status, indication for Flupirtine prescription
- Flupirtine exposure:
 - Number of Flupirtine prescriptions per patient during the 12-month observation period
 - Recommended daily Flupirtine dose (by physicians)
 - Recommended Flupirtine treatment duration (by physicians)
 - Prescription length
 - Indications related to the Flupirtine prescription
 - Co diagnosis within analysis period
 - Concomitant prescription of drugs grouped by relevant ATC classes (Annex 3- ii)
- Administered long-term medications (>14 days) leading to contraindication use of Flupirtine
- Contraindications for use of NSAIDs or weak opioids
- Treatment patterns if available
- Liverfunctions test performed within 1 week after Flupirtine exposure start

9. Research methods

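### The one-week liver-test window closes as the first check after a full week of treatment falls due, so the pre-post comparison may understate uptake of the 2013 monitoring rule

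*Protocol*

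**What the plan says.** The monitoring requirement appears twice. Section 4 (Rationale and background) gives it as "after each full week of treatment patients' liver function should be checked", alongside "treatment duration limited to not longer than 2 weeks". Section 7 gives it as "Weekly liver function tests during treatment and discontinuation in the case of abnormal liver function tests or clinical symptoms".

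The measure is fixed in Section 9.7.2.3: "The proportion of prescriptions with at least one liver function tests within 1 week after prescription date of flupirtine will be estimated". The same one-week limit appears in the Section 4 objectives, in Section 8 ("Liverfunctions test performed within 1 week after Flupirtine exposure start") and in Section 9.3. Section 8 anchors it to exposure start, Section 9.7.2.3 to each prescription date.

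The comparison of 2012 with 2014 in Section 9.7.2.4 names a differently worded parameter, "Number and percentage of prescriptions with LFT monitoring during flupirtine treatment", and gives it no window.

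For orthopaedists, Section 9.7.2.3 admits laboratory data to the analysis only above a threshold: "A minimum number of 100 laboratory test results per time period will be considered as sufficient". The reason given is that laboratory tests are less completely covered in the specialist panels.

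**The concern.** Liver-test monitoring is one of six parameters in the pre-post comparison and the one tied most directly to the hepatotoxicity signal behind the restriction. If the first check is due once a full week has been completed, a window that ends one week after the prescription date stops counting just as that check becomes due. A prescriber who follows the rule and sees the patient on day 8 or 9 is recorded as not having monitored. A test in the first days, before any full week of treatment, is recorded as monitoring.

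Using the same window in 2012 and 2014 does not make the error cancel. The full-week check belongs to the 2013 restrictions, so tests timed to it should be concentrated in 2014. A real improvement could appear smaller than it was.

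A separate, smaller matter is the 100-result rule. It lets the number of tests found decide whether the orthopaedist proportion tested is reported at all.

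**Working it through.** **Inputs from the Protocol.** Check after each full week, treatment limited to 2 weeks (Section 4). Weekly testing during treatment (Section 7). Window of 1 week from the prescription date, counted per prescription (Section 9.7.2.3). Follow-up of one to six months after exposure start (Section 9.2). Expected patients 8,463 (PCP) and 1,365 (orthopaedist) (Table 2). There is no planned liver-test rate to reproduce.

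**Assumptions, not in the Protocol.** s = days from prescription to first dose. A compliant first check is equally likely on any day from 7 + s to 7 + s + k, where k is the scheduling slack. Day 7 counts as inside the window.

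**Step 1: due dates against the window.** With s = 0 the checks fall due on days 7 and 14. The window for that prescription ends on day 7. The first due date is its last day, and the second lies outside it.

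**Step 2: share of compliant first checks counted, Section 4 wording, no repeat prescription.**
c = (number of j in 0..k with 7 + s + j ≤ 7) / (k + 1).

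| s | k = 0 | k = 1 | k = 3 | k = 6 |
|---|---|---|---|---|
| 0 | 100% | 1/2 = 50% | 1/4 = 25% | 1/7 = 14% |
| 1 or more | 0% | 0% | 0% | 0% |

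Under the Section 7 wording a test on any of days 1 to 7 could comply, and all of these are counted. The possible range is therefore 0% to 100%, and the Protocol has nothing to narrow it.

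**Step 3: repeat prescriptions.** A repeat issued on day r opens a window from r to r + 7. A test on day d (8 to 14) is counted under the repeat if d − 7 ≤ r ≤ d. The first prescription still counts as unmonitored.

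**Step 4: net direction.** Let A be the share of prescriptions with a compliant first check, c as above, and e the share of prescriptions that enter the count only through a test before day 7. Then
recorded = A·c + e, and recorded − true = e − A(1 − c).
Illustration: A = 50% and c = 50% give 25% + e. The error is downward if e is below 0.50 × 0.50 = 25% and upward if it is above. The Protocol gives none of A, c or e.

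**Step 5: would the confidence interval reveal it?** Half-width = 1.96·√(p(1 − p)/n), taking one prescription per patient and e = 0:
- p = 25%: 0.9 points (n = 8,463), 2.3 points (n = 1,365).
- p = 12.5% (A = 50%, c = 25%): 0.7 and 1.8 points.

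In this illustration the shortfall is 25 or 37.5 points. A systematic error of that kind would not show in the interval.

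**Step 6: the 100-result rule.** Section 9.7.2.3 lists five analytes and does not say whether each counts as one result. If it does and all five are always run, 100 results come from 100/5 = 20 patients: 20/1,365 = 1.5% (Wilson 95% CI 1.0 to 2.3%). If each patient contributes one result, the largest suppressed count is 99/1,365 = 7.3% (6.0 to 8.8%). Both use the planning count as denominator with one prescription per patient. Proportions of this size can be estimated with useful precision, but the interval does not cover incomplete capture.

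**The case against.** The strongest reply is that Section 7 asks for weekly tests, so a test in the first week complies and is counted. A day-7 test also counts if the window is inclusive. This stands as a limit: the loss is not total, and on that reading the first check is measured properly. It does not remove the conflict with Section 4, and the window still cannot describe monitoring during treatment that runs beyond a week.

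The per-prescription unit also softens the problem, because repeats reopen the window. That is correct for patients with repeats, but not for single prescriptions.

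A reader might infer that the rule biases adherence downward, or that some stated fraction of compliant tests is lost. The documents support neither. They contain no test timing, and early tests push the count upward (Step 4).

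A reader might also infer that under the 100-result rule the number of tests is itself the outcome, so that poor monitoring removes itself from the report. That goes too far. Section 9.7.2.3 bases the rule on limited laboratory coverage, and Section 9.9 says that care outside the practice is not recorded. Few results may mean poor capture rather than poor monitoring. What remains is that suppressing the proportion hides both, and that one period below the threshold prevents the comparison.

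The study is descriptive, with no hypothesis tests and no designated primary endpoint, and an SAP may add detail. But the one-week window is fixed in the Protocol in several places, so an SAP that follows it inherits the problem. Section 9.9 does not list it as a limitation.

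**Conclusion.** The concern holds as a mismatch between the monitoring requirement and its measure. On the Section 4 wording the window ends on the day the first check falls due. Later first checks are missed unless a repeat prescription captures them, and tests before a full week can count. The Section 9.7.2.4 parameter has broader wording and no definition to repair this.

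The consequence for the comparison is that uptake of the 2013 rule may be understated, because tests timed to it would be missed mainly in 2014. This assumes that few 2012 tests followed a full-week schedule, and that the restriction did not also prompt many more tests in the first days. The size, and the net direction of the error in absolute adherence, cannot be derived; the percentages above illustrate and do not estimate. On the 100-result rule, the supportable conclusion is only that the orthopaedist proportion should be reported with a caveat.

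**What to change.** 1. Reconcile Sections 4, 7, 9.7.2.3 and 9.7.2.4 (and the one-week wording in the Section 4 objectives, 8 and 9.3), so that the requirement and the parameter are described in one way. This concerns a measurement definition; it does not say which clinical wording is right.
2. Use one fixed window, identical in 2012 and 2014, that extends past the first due date. An example is at least one listed test from day 1 to day 14 after the prescription date, among prescriptions with at least 7 days of supply. A fixed window is preferable to one tied to prescription length or episode: if the restriction shortened episodes, such a window would be shorter in 2014 than in 2012 and would pick up fewer incidental tests there.
3. Keep the current one-week count as a secondary measure.
4. Report the orthopaedist proportion tested, with its CI and a caveat on laboratory capture, in both periods. Apply the 100-result threshold only to tabulating test values.

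The cost is protocol and SAP wording and one reprogrammed window. Planned follow-up already covers the added days, and prescription length is already derived. The downside is that a longer window also catches some tests done for other reasons or after treatment has ended. It also still counts tests on days 1 to 6, and shows whether any check was made rather than whether every weekly check was.
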